The maximum dose of 115 pmol/kg was chosen because it provides a safety margin of approximately 10X (based on body weight) from the single-dose GLP IV rat study NOAEL. In this study, acute myocardial necrosis was observed at the mid and high doses. By day 15, repair of the myocardium at these doses was almost complete, with only scattered minimal to mild areas of immature connective tissue (fibroplasia) remaining. This is an anticipated pharmacologic effect of potent vasodilators in

nonclinical species: potent vasodilating drugs when administered at high doses to rats are known to produce necrosis and inflammation of the myocardium and cardiac arteries (Greaves, 2012). This is a rat-specific finding not known to translate to humans.

As the dose will be increased and the possible number of subjects exposed to PACAP-38 may also increase, additional risk mitigation steps have been added in order to ensure subject safety throughout the duration of the study. These include measurement of cardiac enzymes (Troponin T and CK-MB) pre-dose, and then at 2 hours, 4 hours, 8 hours and 24 hours after PACAP-38 dosing, and the addition of an ECG 48 hours after PACAP-38 dosing. Stopping rules have also been modified to include potential of PACAP-38 to decrease BP and are now as follows:

- Blood pressure:
 - Systolic BP > 150 mm Hg OR
 - Diastolic BP > 100 mm Hg OR
 - Decrease in SBP from baseline > 30 mm Hg OR
 - Decrease in DBP from baseline > 15 mm Hg and considered clinically relevant after consultation between the investigator and the medical monitor
- Mean heart rate increase of subjects in a given cohort is greater than 50% or greater than 20% decrease over baseline during a 2 hour period after dosing
- Changes in other vital signs or clinical laboratory results considered to pose a significant health risk to subjects

To date, IV PACAP-38 has been found to be safe and well tolerated with subjects experiencing the anticipated PD effects.

Safety: In the 3 cohorts dosed, the safety profile has been consistent with the exerted pharmacological effects of PACAP-38. Majority of reported events were CTCAE Grade 1. The following adverse events were assessed as being CTCAE Grade 2: feeling of pressure on the head (n=1), dry eyes (n=2), MLA (n=1), facial flushing (n=1), muscular tension in the face (n=1) and headache (n=2). Transient effects on blood pressure and heart rate were noted in subjects, however none met stopping criteria.

This amendment is designed to select a PACAP-38 dose that triggers migraine-like attacks, and to ensure subject safety with the fewest adverse events. Previous studies have shown that administration of pituitary adenylate cyclase-activating polypeptide-38 (PACAP-38) formulation will trigger migraine-like headaches in migraineurs (Schytz et al, Brain 2009; Amin et al, Cephalagia 2011; Amin, Brain 2014). In these studies, 10 pmol/kg/min over 20 minutes (total dose 200 pmol/kg) was administered and 66% of migraineurs experienced migraine-like attacks with a median time of headache onset of 4 hours. As PACAP-38 is involved in various biological processes, including sensory processing, vasodilation, inflammation, and nociceptive transmission (Dickinson et al., 1999; Vaudry et al., 2000), both the healthy subjects and migraineurs also experienced the expected adverse events of flushing, heat sensation, along with a transient elevation in heart rate and systolic blood pressure (Birk et al, Regulatory Peptides 2007; Schytz et al, Brain 2009; Amin et al, Cephalagia 2011; Amin, Brain 2014).

The assay values observed during Amgen's replication testing of the PACAP-38 formulation used in the aforementioned published clinical studies, suggest that a significant amount of the PACAP-38 polypeptide binds to the product container surfaces. Although the data were variable, it is estimated that approximately 50% of the peptide may have been lost to surface binding. Amgen formulation modifications using human serum albumin and acetic acid have reduced this problem.

Therefore, in order to ensure subject safety and select the lowest PACAP-38 dose that will trigger moderate to severe migraine-like headaches, a sentinel dosing strategy, along with a Dose-Level Review Meeting (DLRM) has been implemented in this

amendment. The highest dose tested in the sentinel cohorts will be 50% lower than the dose used in the published studies. There will be a total of 3 sentinel cohorts each with a total of 2 subjects who both receive PACAP-38. The starting dose will be an infusion of 10 pmol/kg/min over 2.5 minutes (total dose 25 pmol/kg) for Cohort 1 and 10 pmol/kg/min over 5 minutes (total dose 50 pmol/kg) for Cohort 2 sentinel subjects. Cohort 3 may be enrolled following an informal safety meeting between the principal investigator (PI), medical monitor (MM), and global safety officer (GSO). At that time, available vital signs and adverse events occurring up to 24 hours following PACAP-38 dosing for Cohorts 1 and 2 will be reviewed. Cohort 3 will then receive 10 pmol/kg/min over 10 minutes (total dose 100 pmol/kg). Following Cohort 3, a Dose-Level-Review Meeting (DLRM) will occur to determine the dose of PACAP-38 to be used in the randomized portion of the study.

A high level summary of the adverse events observed in the published human PACAP-38 challenge studies is provided in the background section. Lastly, the eligibility criteria have been modified to ensure that only cardiovascularly healthy migraineurs are enrolled in the study.

Additional updates were made to be in alignment with the newly available protocol template language.

Minor administrative, typographical, and grammatical changes were made.

Dated: 17 May 2017 Page 6

1. Introduction

The purpose of this statistical analysis plan (SAP) is to provide details of the statistical analyses that have been outlined within the AMG 334 Study 20140207 Protocol Amendment 4 (dated 21 Oct 2016), entitled "Phase I, Randomized, Parallel-group, Double-Blind, Placebo-Controlled, Single Dose Study to Evaluate the Blockade of CGRP Receptor by AMG 334 in Preventing PACAP-38 Induced Migraine-like Attacks in Migraine Patients". The scope of this plan includes the interim analysis and the final analyses that are planned and will be executed by the Global Biostatistical Science (GBS) department unless otherwise specified (eg, standard pharmacokinetic (PK) tables will be provided by Clinical Pharmacology Modeling and Simulation [CPMS]).

2. Objectives

2.1 Primary

To evaluate the inhibition of PACAP-38 induced migraine-like attacks by AMG 334

2.2 Secondary

- To evaluate the inhibition of PACAP-38 induced headaches by AMG 334
- To evaluate the safety, tolerability, pharmacokinetics, and immunogenicity of a single intravenous (IV) dose of AMG 334 in migraine patients

2.3 Exploratory

- To evaluate the reduction in severity of PACAP-38 induced migraine-like attacks and headaches by AMG 334
- To evaluate the duration of PACAP-38 induced migraine-like attacks and headaches by AMG 334
- To evaluate the safety and tolerability of a single intravenous (IV) dose of exogenous PACAP-38
- To evaluate CGRP and PACAP-38 levels in migraine patients

3. Study Overview

3.1 Study Design

This is a randomized, double-blind, placebo-controlled, parallel-group study in subjects with episodic migraines. This study will evaluate the efficacy of AMG 334 as measured by inhibition of PACAP-38 induced migraine-like attacks (MLA) after a single dose of AMG 334. MLAs will be defined as attacks fulfilling one of the two criteria:

- (1) Headache fulfilling criteria C and D for migraine without aura (IHS 2004)
 - C. Headache has at least two of the following characteristics:
 - unilateral location
 - pulsating quality

Statistical Analysis Plan: 20140207

Dated: 17 May 2017 Page 7

 moderate or severe pain intensity (≥ 4 on headache questionnaire)

- aggravation by or causing avoidance of routine physical activity
- D. During headache at least one of the following:
 - nausea and/or vomiting
 - photophobia and phonophobia
- (2) Headache described as mimicking usual migraine attack treated with triptan.

Part A: PACAP-38 Dose Selection Phase: In order to ensure subject safety and select the lowest PACAP-38 dose that will ideally trigger headache in all subjects within a given cohort and moderate to severe MLA in the majority of the subjects within the same cohort, a dose selection strategy, along with Safety Review Meetings and Dose-Level Review Meetings (DLRM) have been implemented. Dosing of PACAP-38 shall not exceed a total dose of 115 pmol/kg, providing an approximate 10X exposure margin over the non-clinical NOAEL dose. However, the trigger of headaches in the majority of the subjects within a given cohort and mild, moderate or severe MLAs in the majority of the subjects within the same cohort may be considered acceptable to advance to the randomized portion of the study (Part B).

Up to five cohorts consisting of approximately 2 to 5 subjects are planned. Based on emerging safety and tolerability data, as well as the number of subjects experiencing a headache and/or MLA, the voting members of the Safety Review Meetings or DLRM, may decide cohorts should be removed or additional cohorts should be added, with a maximum of 5 total cohorts. Subject numbers within each cohort may also be increased or decreased based on the decision from the Safety Review Meeting or DLRM. Doses to be administered within each cohort may be repeated, higher or lower than the last dosed cohort. Dosing of any subject shall not exceed 115 pmol/kg.

On Day 1, approximately 2 subjects in Cohort 1 will receive an infusion of 10 pmol/kg/min over 2.5 minutes (total dose 25 pmol/kg). The Principal Investigator (PI) will be responsible to review heart rate (HR) and blood pressure (BP). The BP assessment is based on a single measurement of systolic blood pressure (SBP) of >150 mm Hg or diastolic blood pressure (DBP) >100 mm Hg. If the mean HR increase of the subjects in Cohort 1 is greater than 50% over baseline during a 2 hour period after dosing and SBP does not increase to >150 mm Hg or DBP to >100 mm Hg, then approximately 3 subjects in Cohort 2 will receive an infusion of 10 pmol/kg/min over 5 minutes (total dose 50 pmol/kg). Written documentation from Amgen of the decision to

Statistical Analysis Plan: 20140207

Dated: 17 May 2017 Page 8

proceed with enrollment in Cohort 2 is required. After dosing Cohort 2 and any subsequent cohort, the PI will again be responsible to review HR and BP using previously outlined criteria. These same criteria shall also be assessed for Cohort 3.

After dosing Cohort 3, up to 5 subjects in Cohort 4 will receive 10 pmol/kg/min over 10 minutes (total dose 100 pmol/kg). Following Cohort 4, a DLRM will occur to decide the dose of PACAP-38 to be used in the randomized portion of the study (Part B). This decision will be primarily based on safety and tolerability data, and number of subjects experiencing a headache and/or MLA in Cohort 4, although all of the available data for Cohorts 1 to 4 will be reviewed. The dose-selection for Part B will be based on the goal of ensuring subject safety and ideally triggering headache in all subjects within a given cohort and moderate to severe MLAs in the majority of subjects within the same cohort. However, the trigger of headaches in the majority of subjects within the same cohort and mild, moderate or severe MLAs in the majority of subjects within the same cohort may be considered acceptable to advance to the randomized portion of the study (Part B). If this goal is not achieved, following the DLRM review of the Cohort 4 data, then Cohort 5 dosing of 10pmol/kg/ min over 11.5 minutes (total dose 115 pmol/kg) can commence.

Cohorts 2, 3 and 4 enrollment will occur after a Safety Review Meeting between the principal investigator (PI), medical monitor (MM), and global safety officer (GSO) or designee. At that time, available vital signs and adverse events occurring at least 24 hours following PACAP-38 dosing will be reviewed.

If the PI, MM, and GSO or designee decides not to proceed with enrollment into a subsequent cohort, then a Safety Review Meeting or DLRM will be held after the last dosed cohort. The Safety Review Meeting or DLRM voting members will decide whether or not to proceed with enrollment in Part B Randomization (AMG 334 or Placebo) Phase and if the decision is made to proceed, the Safety Review Meeting or DLRM voting members will select the appropriate PACAP-38 dose from the Dose Selection Phase, Part A. The decision to proceed with Part B of the study will be based on the goal of ensuring subject safety and ideally triggering headache in all subjects within a given cohort and moderate to severe MLAs in the majority of subjects within the same cohort. However, the trigger of headaches in the majority of subjects within the same cohort and mild, moderate or severe MLAs in the majority of subjects within the same cohort may be considered acceptable to advance to Part B of the study.

Part B: Randomization (AMG 334 or Placebo) Phase: PACAP-38 responders from part A, as well as PACAP-38 naïve subjects (those who never received PACAP-38

Statistical Analysis Plan: 20140207

Dated: 17 May 2017 Page 9

before) can enter screening in part B. Subjects will be enrolled in Part B following the 21 day screening period. There will be a minimum duration of 2 weeks between the first and second PACAP-38 doses for all subjects enrolling in Part B of the study.

Eligible PACAP-38 responders from Part A will immediately be randomized to receive either AMG 334 or placebo, whereas eligible PACAP-38 naïve subjects will first enter a PACAP-38 challenge phase. Only PACAP-38 responders (those who experienced a MLA within 24 hours after the challenge) will be randomized to receive either AMG 334 or placebo.

A minimum of 16 and a maximum of 36 PACAP-38 responders will be randomized to receive AMG 334 or Placebo.

PACAP-38 Responders from Part A

On Day 1, PACAP-38 responders from Part A will receive 140 mg IV AMG 334 over 30 minutes or placebo, in a one to one allocation ratio. On Day 8, the subjects will be administered the dose of PACAP-38 determined from the PACAP-38 Dose Selection Phase (Part A).

PACAP-38 Naïve Subjects

On Phase 1 Day 1 (Challenge Period), PACAP-38 naïve subjects will receive the dose of PACAP-38 determined from the PACAP-38 Dose Selection Phase (part A) and will be followed until Day 8. For subjects that do not experience a MLA within 24 hours following PACAP-38 administration (non-responders), Day 8 will be their End of Study (EOS) visit. Those subjects who experience a MLA within 24 hours following PACAP-38 (responders) will be randomized to receive 140 mg IV AMG 334 over 30 minutes or placebo on Phase 2 Day 1 (Treatment Period), in a one to one allocation ratio. On Day 8, the PACAP-38 responders will be administered the dose of PACAP-38 determined from the PACAP-38 Dose Selection Phase (part A).

All subjects will remain in-house for 24 hours of observation following PACAP-38 infusion. Subjects (respectively PACAP-38 responders from part A and PACAP-naïve subjects) will be followed until Day 85.

Subjects will be monitored and asked questions from the headache questionnaire, as per the Schedule of Assessment in Table 2 of Protocol Amendment 4, to determine if they have experienced a MLA. Previous challenge studies have shown that for migraineurs the median onset of a MLA is within 4 hours with some patients experiencing a MLA as late as 12 hours following PACAP-38 infusion. Therefore, a

Statistical Analysis Plan: 20140207

Dated: 17 May 2017 Page 10

[figure not shown]
headache questionnaire covering the 24 hours after infusion will ensure capture of all the PACAP-38 induced MLAs. After 24 hours of data from the first 16 randomized (AMG 334 or Placebo) subjects challenged with PACAP-38 is available, an interim analysis will be conducted to determine if challenge rates are comparable to historical rates (~66%) and if AMG 334 has greater efficacy than placebo. If AMG 334 is found to completely block PACAP-38 induced migraines, or have the same efficacy as placebo, the study will be terminated. Otherwise, approximately 20 randomized (AMG 334 or Placebo) subjects will be added.

The overall study design is described in the study schema below:

Statistical Analysis Plan: 20140207

Date: 17 May 2017

Abbreviations:

[figure not shown]
DLRM = Dose Level Review Meeting IV = Intravenous

Page 11

Statistical Analysis Plan: 20140207

Date: 17 May 2017 Page 12

Statistical Analysis Plan: 20140207

Date: 17 May 2017 Page 13

3.2 Sample Size

Up to 25 subjects may participate in Part A. An adequate number of migraine subjects are planned to be randomized and enrolled into Part B of the study, in order to obtain 16 PACAP-38 responders to participate in the interim analysis and depending on those results an additional 20 PACAP-38 responders to complete the study. If ambiguous results in Part A occur regarding the ability of PACAP-38 to ideally safely trigger a headache in all subjects within a given cohort (although, safely triggering headaches in the majority of subjects within a given cohort may be considered acceptable to advance to Part B of the study) and mild, moderate or severe MLAs in the majority of subjects within the same cohort, then a previously dosed cohort sample size may be expanded to up to 5 subjects per cohort. Once the PACAP-38 dose has been selected, enrollment in part B can start. The data collected for the 16 subjects that received AMG 334 or Placebo will be included in the interim analysis. Following the interim analysis, if the decision is to continue enrollment for the study, an additional 10 subjects will be planned to receive placebo, and another 10 subjects to receive AMG 334.

The sample size is not based on any power calculations; it is based on practical considerations and is consistent with this type of study. The results from 10,000 simulated trials demonstrate that, if, PACAP-38 produces MLA in 70% of placebo treated PACAP-38 responders, and AMG 334 is effective in blocking MLA such that only 20% of AMG 334 treated subjects have a headache, then there is approximately a 91% chance of overall trial success (see Section 8 for more details).

4. Study Endpoints and Covariates

4.1 Study Endpoints

Primary Endpoints:

• Occurrence of a MLA within 24 hours of challenge-agent infusion

Secondary Endpoint(s):

- Occurrence of a headache within 24 hours of challenge-agent infusion
- Treatment-emergent AE
- Clinical significant changes in vital signs, ECGs, physical examinations, laboratory safety tests, and neurological assessments
- AMG 334 PK parameters, including C₁ hour and AUC_{84d}
- Anti-AMG 334 antibodies

Statistical Analysis Plan: 20140207

Date: 17 May 2017 Page 14

Exploratory Endpoint(s):

• Severity of PACAP-38 induced MLA and headaches

- Duration of PACAP-38 induced MLA and headaches
- Migraine characteristics: localization, accompanying symptoms and pre-monitory symptoms.
- PACAP-38 related treatment-emergent AE
- Evaluate the concentration of PACAP-38 and CGRP following administration of AMG 334

4.2 Planned Covariates and Subgroups

Planned covariates consist of baseline measures. No subgroup analysis is planned.

5. Hypotheses and/or Estimations

A single dose of 140 mg IV of AMG 334 will inhibit MLAs in subjects challenged with PACAP-38.

6. Definitions

Adverse Event (AE)

Serious Adverse Event (SAE):

SAE determined by the flag indicating if the adverse events is serious on the AE eCRF page will include these that occur after signing the informed consent and up to and including end of study (EOS).

Treatment-Emergent AE:

A treatment-emergent AE is that occurs on or after the initial dose of investigational product (IP) as determined by the flag indicating if the AE started prior to the first dose on the AE eCRF and up to and including end of study.

Disease-Related AE:

Migraine will be considered a disease related event; however, worsening of migraines (ie. increased frequency and/or intensity) should be reported as an AE.

Baseline

Unless otherwise stated, baseline will be defined as the last assessment taken prior to the first IP (AMG 334 or placebo) administration (ie, Day 1 pre-dose or Screening if Day 1 pre-dose is not available).

Statistical Analysis Plan: 20140207

Date: 17 May 2017 Page 15

Change from Baseline:

The arithmetic difference between a post-baseline value and the baseline value:

Change (absolute) from Baseline = (Post-baseline Value – Baseline Value)

Change (percent) from Baseline = [(Post-baseline Value – Baseline Value) / Baseline Value] x 100

Body Mass Index (BMI)

BMI will be calculated as {weight (kg)/ [height (m)]²} in the clinical database.

Columbia Suicide Severity Rating Scale (C-SSRS)

The C-SSRS is a clinical rating of suicidal ideation and behavior. Refer to Appendix E and Appendix F in the protocol for complete details on the C-SSRS. The Baseline/Screening version of the C-SSRS will be administered at screening (Day -21 to -2), while the Since Last Visit version of the C-SSRS will be administered at the other time point(s) on the Schedule of Assessments. Reports of suicidal ideation with intent to act (endorse item 4 or 5) and reports of actual, aborted, or interrupted suicide attempts or a behavior preparatory for making an attempt indicate subjects at high risk for suicide. If such reports are identified, the investigator is to appropriately manage the subject in accordance with standard of care.

End-of-Study (EOS)

The EOS is the last planned clinical visit for each subject enrolled in this study.

Primary Completion:

Defined as the time when the last subject is assessed or receives an intervention for the purposes of final collection of data for the primary analysis (ie., when the last subject completes the migraine questionnaire 24 hours after challenge agent (PACAP-38) administration or is discontinued from the study).

End of Trial:

Defined as the time when the last subject is assessed or receives an intervention for evaluation in the study (ie., when the last subject completes the study, which includes the safety follow-up visit 11 weeks after the challenge agent (PACAP-38) administration, or is discontinued from the study).

Statistical Analysis Plan: 20140207

Date: 17 May 2017 Page 16

Subject-level EOS Date

EOS for each subject is defined as the date the subject last participated in the study.

The date will be recorded on the EOS case report form (CRF) page.

Enrollment

A subject will be considered enrolled when the investigator decides that the subject has met all eligibility criteria. Enrollment Date is defined as the date collected on the CRF.

Investigational Product (IP)

The term IP is used in reference to AMG 334 or placebo.

PACAP-38

Pituitary adenylate cyclase-activating polypeptides-38 is a neuropeptide belonging to the VIP/secretin/glucagon superfamily. PACAP-38 is a non-investigational medicinal product (NIMP) and used as a challenge agent.

Randomization Date

The day the subject was assigned a randomization number.

Study Day 1

Day 1 is defined as the first day that IP is administered to the subject. The day before Day 1 is referenced as Day-1.

Study Day

Post day of dose: study day= (study date - date of study Day 1) +1

Pre day of dose: study day= (study date - date of study Day 1)

The day prior to the first IP dosing is Day –1 while the day of the first IP dose is Day 1.

7. Analysis Subsets

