7.1 Safety Analysis Set

The safety analysis set will consist of all subjects who receive IP (AMG 334 or placebo). Subjects will be analyzed according to the IP received (AMG 334 or Placebo).

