10.1 General Principles

Unless otherwise stated, data from PACAP-38 responders who go on to be randomized and receive IP will be summarized. Data from PACAP-38 non-responders, and data from

Statistical Analysis Plan: 20140207

Date: 17 May 2017 Page 22

PACAP-38 responders that do not receive IP, will not be included in the summaries, but will be reviewed.

Unless otherwise specified, data will be summarized using the safety analysis set, by actual treatment group (AMG 334 or Placebo).

Descriptive statistics will be provided for selected demographics, safety and PK data. Descriptive statistics on continuous measurements will include means, medians, standard deviations (and standard errors for post-baseline data), quartiles, and ranges, while categorical data will be summarized using frequency counts and percentages. Where statistical models are applied to the data, estimates of the differences/ratios, confidence intervals and corresponding p-values will be presented, as applicable. However, these are for descriptive and illustrative purposes only and to aid interpretation of the data; no formal statistical hypothesis testing will be performed.

When data are summarized by time, the values recorded against the scheduled time points, including any time windows specified in the protocol will be used.

When assessing minimum/maximum increases or decreases over the study, all assessments, including unscheduled assessments will be used.

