10.6.2 Safety Endpoints

10.6.2.1 Adverse Events (AEs)

The Medical Dictionary for Regulatory Activities (MedDRA) version 19.1 or later will be used to code all AE to a system organ class and a preferred term. The subject incidence of AEs will be summarized for all treatment-emergent, serious treatment-emergent, those leading to withdrawal of IP, fatal, and events of interest (EOI), where treatment refers to IP. The identification of EOI is a continuous process. Events may be identified and documented as the safety profile of the drug is characterized. The severity of each AE will be graded using common terminology for AE (CTCAE) version 4.0 criteria.

Statistical Analysis Plan: 20140207

Date: 17 May 2017 Page 24

Subject incidence of all treatment-emergent, serious treatment-emergent, those leading to withdrawal of IP, and fatal AE will be tabulated by system organ class and preferred term, where treatment refers to IP. Where appropriate, the tables will also be presented by worst grade. The above AE tables will not be created if two or fewer subjects experience the AE. The above AE tables will be summarized separately for events occurring between Day 1 and Day 7 following administration of IP and events occurring from Day 8 onwards following administration of IP and the second dose of PACAP-38.

For PACAP-38 related treatment-emergent AEs, all treatment-emergent AEs where the question "Is there a reasonable possibility that the event may have been caused by PACAP-38?" is ticked "yes" will be summarized by treatment group.

Details of each AE will be listed.

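### The SAP tabulates adverse events only from the AMG 334/placebo dose onward, so events at first PACAP-38 exposure are listed or reviewed but never summarised; the HR/BP change after the challenge also lacks a pre-infusion baseline.

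*SAP*

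**What the plan says.** **Adverse events.** SAP Section 2.3 lists among the exploratory objectives: "To evaluate the safety and tolerability of a single intravenous (IV) dose of exogenous PACAP-38". The matching endpoint in Section 4.1 is PACAP-38-related treatment-emergent AEs.

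Four rules decide which events reach a table:

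- Section 6, start of the AE period: "A treatment-emergent AE is that occurs on or after the initial dose of investigational product (IP".
- Section 6, meaning of IP: "The term IP is used in reference to AMG 334 or placebo". PACAP-38 is classed separately, as a non-investigational product.
- Section 7.1, analysis set: "The safety analysis set will consist of all subjects who receive IP (AMG 334 or placebo".
- Section 10.1, data used: "data from PACAP-38 responders who go on to be randomized and receive IP will be summarized". Non-responders' data are set aside, and so are those of "PACAP-38 responders that do not receive IP, will not be included in the summaries, but will be reviewed".

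Section 10.6.2.1 then says "Subject incidence of all treatment-emergent, serious treatment-emergent, those leading to withdrawal of IP, and fatal AE will be tabulated", with the qualifier "where treatment refers to IP". The PACAP-38-related summary is drawn from the same treatment-emergent events, by treatment group. Every AE is also listed.

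**HR and BP.** Section 10.6.2.2 plans summaries over time and change from baseline and names no baseline. The Section 6 default applies: the last value before the first IP dose, normally Day 1 pre-dose.

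**The concern.** SAP Section 3.1 gives every randomised subject a PACAP-38 infusion before IP, either in Part A or in the challenge phase for naive subjects. Challenge-phase non-responders leave at Day 8 without IP. An AE clock that starts at IP therefore misses every first exposure, including those of subjects who are later randomised.

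At stake is the tolerability objective. The tables would describe PACAP-38 only at a second dose and only in people already shown to respond to it. AE incidence at first exposure, by PACAP-38 dose, is the most direct answer to the objective and is not a planned output. The nearest available figures, in Protocol Section 2.4, are pooled over 7 Part A subjects.

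For HR and BP, the effect of interest after the challenge is the change from just before the infusion. The default baseline precedes the Day 8 challenge by at least 8 − 1 = 7 days, so it mixes the acute response with a week of drift and any effect of AMG 334.

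**Working it through.** The documents give no coverage figure to reproduce. The check traces the definitions and then sizes the gap.

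**1. Trace by type of exposure**

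| Exposure | Before or after IP | In AE tables? |
|---|---|---|
| Part A infusion | before, or no IP at all | no |
| Challenge-phase infusion, non-responder | no IP | no |
| Challenge-phase infusion, responder | before | no |
| Day 8 infusion after AMG 334 or placebo | after | yes, by arm |

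Serious AEs do not close the gap. They are collected from consent (SAP Section 6) but tabulated only as serious treatment-emergent events.

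**2. Ceiling without assumptions.** Each of the N randomised subjects has one earlier, untabulated infusion. Coverage is at most N/(N + N) = 50%, and coverage of first exposures is zero.

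**3. Illustration with assumptions**

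- N = 16 or 36 (SAP Section 3.1).
- A = Part A subjects, 11 to 25. The 11 are 2 in Cohort 1 (Protocol Section 2.4) plus 9 at the higher doses (Amendment 3 summary). The 25 is the maximum in SAP Section 3.2.
- r = responder rate, assumed 0.50 to 0.70. The lower value is the roughly one-half reported in the Amendment 3 summary. The upper value borrows the 70% planning figure in SAP Section 3.2. Neither is a rate in naive subjects at the selected dose.
- k = Part A responders who re-enter, from none to all.
- Cap on k: Cohorts 1 to 3 had 0, 2 and 1 attacks (Protocol Section 2.4). Two of the 9 later subjects had no headache, and one of those was in Cohort 3. All three Cohort 2 subjects had a headache or an attack, so the other was in Cohort 4, which leaves at most 3 attacks among its 4 subjects. The known 11 therefore hold at most 0 + 2 + 1 + 3 = 6 responders, and k ≤ 6 + floor(r(A − 11)), and never more than floor(rA) or N.

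First exposures F = A + (N − k)/r. Total infusions = F + N. Coverage = N/(F + N).

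| N | Case | F | Total | Coverage |
|---|---|---|---|---|
| 16 | A=25, r=0.5, k=0 | 25 + 16/0.5 = 57 | 73 | 21.9% |
| 16 | A=11, r=0.7, k=6 | 11 + 10/0.7 = 25.3 | 41.3 | 38.8% |
| 36 | A=25, r=0.5, k=0 | 25 + 36/0.5 = 97 | 133 | 27.1% |
| 36 | A=11, r=0.7, k=6 | 11 + 30/0.7 = 53.9 | 89.9 | 40.1% |

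These are the extremes over the whole grid. The 7 subjects in Protocol Section 2.4 are 7/97 = 7.2% to 7/25.3 = 27.7% of first exposures.

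**4. HR and BP.** The mean acute change at time t equals the mean at t minus the Day 8 pre-infusion mean, if the same subjects contribute to both. The variance of that change is Var(t) + Var(pre) − 2Cov(t, pre). The covariance is in no planned output, so neither the spread nor the individual changes can be recovered. With invented heart rates of 70 on Day 1, 60 before the infusion and 100 at peak, the rise is 30/70 = 42.9% on the SAP baseline and 40/60 = 66.7% on the pre-infusion value.

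**The case against.** The strongest defence is that the declared endpoint is analysed. PACAP-38-related treatment-emergent AEs are summarised by arm, and the placebo column shows PACAP-38 without AMG 334. That stands. A reader might infer that PACAP-38 safety has no analysis at all, but the SAP does not support that. What is missing is the first exposure.

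Second, the data are not discarded. All AEs are listed, non-responder data are reviewed, and Part A data go unblinded to the dose-level and safety review meetings (SAP Section 8.1). That stands too, although those meetings serve dosing decisions and a listing gives no incidence by dose. For cohorts of 2 to 5 subjects a table adds little per column, so the gain comes mainly from pooling and from the challenge phase.

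Third, the Part A gap is inherited, because the safety set in Protocol Section 10.1.2.1 already required IP. The naive challenge phase appears only in the SAP. The SAP follows Amendment 4, whereas the protocol supplied is Amendment 3. That protocol's Table 3 records Part A AEs from the infusion, but its Section 9.2.2.1 starts non-serious AE reporting at the first IP dose and its Section 5 at enrolment. Collection in the challenge phase is therefore inferred.

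Fourth, a pre-IP baseline is suitable for AMG 334 safety, and the SAP commits to HR/BP summaries that the protocol left optional. It would be too strong to call that baseline an error or to say the acute response is lost. With complete data its mean can be derived, but its spread and the individual changes cannot.

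**Conclusion.** The point holds in this limited form. By the SAP's own rules, no AE at a first PACAP-38 exposure enters a table, and single-dose PACAP-38 tolerability is tabulated only at a second dose in selected responders. The one size that needs no assumption is the ceiling of 50% of infusions, with no first exposures covered. The ranges of about 22–39% (16 randomised, 25–57 first exposures untabulated, 41–73 infusions) and 27–40% (36 randomised, 54–97 untabulated, 90–133 infusions) are illustrations. They depend on the assumed responder rate, the Part A size and the number re-entering. If only 5 of the 11 known Part A subjects responded, the upper ends fall to 37.5% and 39.4%.

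The HR/BP matter is a separate and smaller omission: a useful second baseline is missing.

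The objective is exploratory and descriptive. The primary comparison uses attacks after the Day 8 infusion and is unaffected. The change is still worth making, because a stated objective otherwise has no first-exposure summary and the remedy is cheap.

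**What to change.** - Add a PACAP-38-exposed set: all subjects with at least one infusion, Parts A and B, responders and non-responders.
- Define PACAP-38-emergent AEs from the start of each infusion.
- Tabulate first exposures by PACAP-38 dose in one table with a pooled column, and the post-IP exposure by arm. A single table also avoids the Section 10.6.2.1 rule that drops a table when two or fewer subjects have the event, which would remove a separate table for a 2-subject cohort.
- Keep the pre-IP baseline for HR and BP, and add a pre-infusion baseline for change after the challenge. The Amendment 3 schedule has Day 8 pre-dose vital signs, and Protocol Section 10.5.3.2 had already taken Day 8 pre-dose as the ECG baseline.
- First confirm in Amendment 4 that challenge-phase AEs and pre-infusion vital signs are collected.

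The cost is SAP wording and a few descriptive tables, with sparse Part A columns. Sample size and error rates do not change.
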